to either (1) record the whole appointment. If this happens the research assistant will only transcribe the dialogue pertaining to prenatal genetic screening, or, (2) to turn on the recorder when the discussion regarding prenatal genetic screening is taking place.

As recent guidelines have changes, we will again be offering patients the option to consent to audio-recording during their first visit for the CCF and MetroHealth sites.

4) QPV: This survey will be administered approximately 7-10 days following the first visit when the basic concepts associated with prenatal genetic testing have been introduced. It will be administered using online REDCap survey. Unless otherwise specified by the participant.

5) QTT: This survey will be administered between weeks 12-22 EGA once the participant has made a decision about if to undergo prenatal genetic testing (or at the EGA at which the opportunity has closed in the case of those participants who elect against testing). It will be administered using online using REDCap survey. Unless otherwise specified by the participant.

6) QFF: This survey will be administered between weeks 22-24 EGA. It will be administered using online using REDCap survey. Unless otherwise specified by the participant.

A review of the medical record will be conducted prior to communication about each survey to ensure that the participant continues to meet inclusion criteria. Individuals who experienced a complication or fetal demise as documented at the time point of QPV, QTT and QFF, or who no longer receive care at the Cleveland Clinic or MetroHealth, depending on original site of enrollment and will not be contacted to complete the survey(s). Each study site, either Cleveland Clinic or MetroHealth, will be responsible for all subsequent chart reviews and administration of all QPV, QTT and QFF surveys for all participants enrolled at those sites. All patients will receive a research stipend of the following amounts for each of the completed surveys from the Cleveland Clinic Accounts Payable Offices (patients will receive up to \$150.00):

- 1) QBASE - \$25.00
- 2) QPV - \$25.00
- 3) QTT - \$50.00
- 4) QFF - \$50.00

II. Partners of participating pregnant patients

We will utilize the same data collection instruments and procedures at both the Cleveland Clinic and MetroHealth.

Data collection instruments: This includes the QBASE and QPV, both identical to the questionnaires administered to pregnant participants.

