Once the OB provider sends back their signed informed consent agreeing to participate in the study, the research coordinator will send the OB provider a link through REDCap. This link will take the OB provider directly to the OBP questionnaire and can complete the survey electronically on any internet connected device, unless otherwise specified (we are able to give the providers hard copy of the survey, and those providers can either scan and email the completed survey to their respective research coordinator or via a fax number provided to them by the research coordinator). Once completed, the study coordinator will have their responses to the survey on the NEST study restricted drive and will move forward with gift card purchase. After the survey is completed and saved, the research coordinator will send a \$50.00 amazon gift card in appreciation to the OB provider for their participation in the study and the completion of their OBP questionnaire. For the MetroHealth providers, the MetroHealth research coordinator will send a weekly report to the Cleveland Clinic research coordinator containing a list of names and emails of the providers that need to be sent their amazon gift card.

For providers assigned to use the NEST communication tool, they will be sent a short feasibility survey (OBP-F) to assess if they are using the NEST. This survey will be sent once the provider has had a respectable amount of time participating in the study.

Due to the presence of COVID-19 in Ohio, we will conduct consenting and survey procedures through electronic options previously approved for CCF. Our MetroHealth sites will be allowed to recruit electronically or in-person based off of the MH research re-installment policy. All follow-up surveys (QPV, QTT, QFF, OBP, OBP-F) will be sent to participants electronically. They will still receive stipends, but we know that there will likely be a delay in the usual turnaround time for the stipends, so when participants complete a survey they will be informed by their site study coordinator (either CCF or MetroHealth) that their survey was received but due to the COVID-19 outbreaks there will likely be a delay for them to receive the stipends.

DATA ANALYSIS

Data Analysis

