Oversight of the study will be provided by the Principal Investigator, [name], and the study co-investigators.

MONITORING PROCEDURES

[name] will ensure that informed consent has been obtained prior to performing any research procedures, that all subjects meet eligibility criteria, and that the study is conducted according to the IRB-approved research plan.

Study data are accessible at all times for the Principal Investigator and co-investigators to review. The Principal Investigator and co-investigators will review the different aspects of the study conduct on a monthly basis. This will include assessment of recruitment, accrual, drop-outs, and any protocol deviations. The Principal Investigator and co-investigators will review the study procedures and data for any Adverse Events (AEs) as defined below, individually in real-time and in aggregate on a monthly basis. The Principal Investigator and co-investigators will review the study procedures and data for any serious adverse events (SAEs) as defined below in real-time. The Principal Investigator will report all protocol deviations, AEs, and SAEs to the NIH and Cleveland Clinic IRB according to the applicable regulatory requirements.

COLLECTION AND REPORTING OF SAEs AND AEs

Definition of an Adverse Event (AE): As this is a clinical trial of a communication tool, the study and safety issues and adverse events observed are expected to be minimal. That said, we have outlined the following Adverse Events for this study based on standard definitions of AEs as any unfavorable and unintended sign (including an abnormal laboratory finding), symptom, or disease temporally associated with the use of a medical treatment or procedure, regardless of whether it is considered related to the medical treatment or procedure.

An AE for this study includes the following:

- Loss of confidentiality of study data between the patient-subject and partner-subject: As described above, the patient-subject and partner-subject will be aware of the decision to participate and aware of the content of discussions that take place as part of direct observation. Both will be informed that there will be no intentional disclosure of information provided on individually completed surveys between the patient-subject and partner-subject.

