- Psychological distress necessitating provider-initiated referral or self-referral to Behavioral Health for counseling at any time point in the study: The process of exploring the nature and implications of prenatal genetic testing may cause distress in any patient presenting for prenatal care. We acknowledge that some participants may experience distress from exploring these decisions differently as part of the intervention versus the control, whether that results in a greater or lesser depth of pre-test and post-test consideration and its relation to decisional regret. We also acknowledge that discussions about the goals and implications of prenatal genetic testing may lead to disagreement and distress between a pregnant patient and her partner. Distress that results in referral to Behavioral Health will be considered an AE. This includes referral within the healthcare system as identified by chart review or verbal report of the subject or subject-initiated referral outside of the healthcare system.

Serious Adverse Event (SAE)

SAEs have been defined in consideration of aspects associated with recruiting a pregnant woman-partner dyad. Given those considerations, any AE that results in any of the following outcomes will be designated as a SAE:

- Suicidal or homicidal ideation with or without action
- Incidence of domestic violence
- Event requiring inpatient hospitalization or prolongation of existing hospitalization

SAEs and specific procedure-associated AEs will be reported to the Data Safety Monitoring Board (DSMB) within 24 hours. In addition, all AEs will be reported according to the Cleveland Clinic IRB AE reporting guidelines.

Classification of AE Severity

AEs will be labeled according to severity, which is based on their impact on the subject according to the following definitions:

Mild: An experience that is transient, and requires no special treatment or intervention. The experience does not generally interfere with usual daily activities. This includes transient laboratory test alterations.

Moderate: An experience that is alleviated with simple therapeutic treatments. The experience impacts usual daily activities. Includes laboratory test alterations indicating injury, but without long-term risk.

Severe: An experience that requires therapeutic intervention. The experience interrupts usual daily activities. If hospitalization (or prolongation of hospitalization) is required for treatment, it becomes an SAE.

AE Attribution Scale

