AEs will be categorized according to the likelihood that they are related to the study intervention. Specifically, they will be labeled not related, possibly related, or related to the study intervention as follows:

Not related: The AE is clearly not related to the study procedures (i.e., another cause of the event is most plausible and/or a clinically plausible temporal sequence is inconsistent with the onset of the event).

Possibly related: An event that follows a reasonable temporal sequence from the initiation of study procedures, but that could readily have been produced by a number of other factors.

Related: The AE is clearly related to the study procedures.

AEs are identified by review of study procedures and the medical record. Review of the medical record will be performed as outlined by the IRB for the purpose of this study to identify any ICD-10 codes or referrals consistent with AEs defined above. AEs will also be identified by verbal report of a subject or subject-initiated referral outside of the healthcare system.

Management of Risks to Subjects

If an AE or SAE is identified, then a process of review of study procedures will take place. This will include review of documentation and storage of materials related to the study. This will also include a review of recruitment and communication practices among the research team to identify if and where possible AEs or SAEs occurred. This will also include review of surveys and transcripts from direct observation to determine the timing and source of the AE or SAE.

AE and SAE Reporting

SAEs and specific study-associated AEs will be reported to the NIH and the Cleveland Clinic IRB within 24 hours. In addition, all AEs will be reported according to the Cleveland Clinic IRB AE reporting guidelines. In addition, all SAEs and specific study-associated AEs will be reported to the Data Safety Monitoring Board.

Data Safety Monitoring Board

A formal, independent Data Safety Monitoring Board (DSMB) has been established with specific expertise in nature of this study and study population to provide oversight for AEs and SAEs. The DSMB will include members with specific disciplinary expertise in:

- 1) Obstetrics and maternal fetal medicine
- 2) Research and clinical ethics
- 3) Clinical genetics
- 4) Clinical trials
- 5) Medical decision-making

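### Self-referral for counselling outside the health system is a defined adverse event, but no follow-up contact is described as asking about it, and the last dated chart check comes before the final survey

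*Combined protocol and SAP*

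**What the plan says.** **Definition.** Under Collection and Reporting of SAEs and AEs, psychological distress that leads to a counselling referral is an AE whenever it occurs during the study. The definition covers referral by a provider, self-referral, and referral that the participant arranges outside the health system. An SAE is any AE with one of three listed outcomes.

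**Detection.** The AE Attribution Scale section gives two routes. First, "AEs are identified by review of study procedures and the medical record"; the record is searched for diagnosis codes and referrals, with the timing left to the IRB's outline. Second, "AEs will also be identified by verbal report of a subject or subject-initiated referral outside of the healthcare system".

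**Review and reporting.** Under Monitoring Procedures the investigators review AEs "individually in real-time and in aggregate on a monthly basis", and they "review the study procedures and data for any serious adverse events (SAEs) as defined below in real-time". Two reporting rules follow: "SAEs and specific procedure-associated AEs will be reported to the Data Safety Monitoring Board (DSMB) within 24 hours", and "SAEs and specific study-associated AEs will be reported to the NIH and the Cleveland Clinic IRB within 24 hours". Neither says what event starts the clock.

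**Follow-up.** Under Data collection procedures for pregnant participants, "A review of the medical record will be conducted prior to communication about each survey"; the stated aim is to confirm that the woman is still eligible. The COVID-19 paragraph in the OB provider section adds: "All follow-up surveys (QPV, QTT, QFF, OBP, OBP-F) will be sent to participants electronically".

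**The concern.** A chart cannot be relied on to show counselling that a woman arranges outside the system. The plan is therefore left with her telling someone, and no scheduled follow-up contact is described as inviting her to do so. For events inside the system, a reader cannot tell from the document how often charts are searched for AEs. The only dated checks have another purpose and stop before the last survey.

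At stake is how a low AE count should be read. The protocol itself recognises that distress may differ between NEST and usual care and may relate to decisional regret, which QTT and QFF measure. If few events are recorded, the Data Safety Monitoring Board (DSMB) cannot separate a tool that causes little distress from a plan that seldom looks for it. Because an SAE is defined as an AE with certain outcomes, the same gap carries over to SAEs.

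**Working it through.** The plan states no maximum interval between chart checks, so there is no figure of its own to reproduce. The check has two parts.

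**1. Is outside self-referral asked about?**

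| Survey | Content listed under Data collection instruments | Distress or referral item listed |
|---|---|---|
| QPV | knowledge, attitudes, decision-making, health literacy | none |
| QTT | knowledge, attitudes, decision-making, decisional regret | none |
| QFF | knowledge, attitudes, decision-making, decisional regret | none |

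None of the three follow-up surveys lists such an item, and no scheduled call or visit after the first prenatal visit is described as asking. The instruments themselves are not reproduced, so this rests on the summaries.

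**2. How far apart are the dated chart checks?**

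Inputs, in weeks of estimated gestational age (EGA):
- First visit: 7 to 12 (inclusion criteria); 9 to 10 in the example under Recruitment Procedures.
- QPV: 7 to 10 days after the visit in the main text, 7 to 9 days in the site procedure lists. The two should be reconciled, but the longest gap depends only on day 7.
- QTT: 12 to 22. QFF: 22 to 24.
- Assumption: each check is made when its survey is sent.

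Longest gap = latest next check − earliest previous check.
- QPV to QTT, earliest entry: 7 + 7/7 = 8; 22 − 8 = **14 weeks** (98 days).
- QPV to QTT, earliest example visit: 9 + 7/7 = 10; 22 − 10 = **12 weeks**.
- QPV to QTT, latest entry and day 10: 12 + 10/7 = 13.43; 22 − 13.43 = 8.57 weeks.
- QTT to QFF: 24 − 12 = **12 weeks**.

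For a woman entering at 7 weeks, the longest gap is max(QTT − 8, QFF − QTT). It is smallest at QTT 15 and QFF 22: max(7, 7) = 7 weeks. It is largest at QTT 22: max(14, QFF − 22) = 14 weeks.

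The last dated check falls at 22 to 24 weeks, which is 22 − 12 = 10 to 24 − 7 = 17 weeks after the first visit. It precedes QFF, so distress prompted by QFF comes after every dated check. The document gives no end to AE observation. If it ran to 40 weeks (an assumption), 40 − 24 = 16 to 40 − 22 = 18 weeks would have no dated check.

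**Partners.** They fall within the safety definitions, but only the pregnant woman's chart is checked before the partner QPV, which is their last contact. Partner recruitment is currently suspended.

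**The case against.** The strongest reply is that the dated checks are not the AE review. They confirm eligibility; the AE search of the record is described separately, with its timing set by the IRB. Data are also open to the investigators at all times, review of study procedures is a further route, and AEs are expected to be minimal in a trial of a communication tool. All of this stands. It means that the AE review interval is unstated, not that it has been shown to be 14 weeks.

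A reader might infer several stronger points that the documents do not support:

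- *AEs are found only at checks 14 weeks apart.* This treats the eligibility schedule as the AE schedule. Fourteen weeks also needs the earliest entry and the latest QTT, whereas QTT is tied to when the woman has decided.
- *Follow-up involves no verbal contact.* A participant may ask for another survey mode. Coordinators tell participants that a survey has arrived, by a means not stated. The sub-study plans about 40 telephone interviews, though only with women who completed the main study.
- *The 24-hour rule is contradicted.* A delay in finding an event and a deadline for reporting it are different quantities. If the clock runs from awareness, the two are compatible.
- *Outside referrals will be near zero by construction.* Women may volunteer them, and no event rate is given.
- *Detection differs by arm.* At Cleveland Clinic, staff attend in person for audio-recording or to give NEST. Audio is offered in both arms, and the NEST contact comes before the first visit, too early to hear of later distress. Scheduled follow-up is the same in both arms.

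None of these replies supplies a question about outside referral or a dated check after QFF.

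**Conclusion.** The point holds as a gap in ascertainment. A defined AE depends on the participant volunteering it. The AE chart-review interval, the start of the 24-hour clock and the end of AE observation are not stated. Outside self-referrals and events after the QFF check may go undetected; in-system events before it may be found late. Review in real time is stated, but no described procedure shows how it would be achieved.

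The size is a listed item on distress or referral in none of the three follow-up surveys, dated checks up to 12 to 14 weeks apart in the extreme, and no dated check after 22 to 24 weeks. The number of events affected cannot be estimated. The conclusion assumes that the survey summaries are complete and that the IRB outline adds no later check or solicited question; either would narrow it. It is an inexpensive improvement to safety ascertainment and does not bear on the primary comparison of shared decision-making.

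**What to change.** **Changes**
1. Add one fixed item to QPV, QTT and QFF, worded identically in both arms, asking whether since the last contact the participant has been referred to or sought counselling or mental-health care, inside or outside the health system. Add it to the partner QPV if partner enrolment resumes.
2. Set a REDCap alert on a positive answer, routed through the Cleveland Clinic coordinator. The MetroHealth data-management text lets that site's staff view only NEST questionnaire data, so an alert sent to them alone could not be followed up in the survey.
3. Add one chart check for AEs at a fixed interval after QFF, for example 30 days. Include women who are no longer sent surveys because of a complication or fetal demise, counting from when QFF would have been due.

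**Clarifications**
- State the AE chart-review interval and the end of AE observation, and make the description of real-time review agree with them.
- State that the 24-hour clock runs from site awareness.

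**Cost.** One survey item, one alert, one more chart look per woman by existing coordinators, and an IRB amendment. More mild events will be recorded. Women who leave the health system receive neither the surveys nor a useful chart check, so for them the gap is not closed.
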